1. BACKGROUND

Surgical site infection (SSI) remains a persistent and morbid problem in colorectal surgery with published rates ranging from 7 to 25%¹⁻⁶. The negative outcomes of SSI are well reported and include a significant increase in morbidity, length of hospital stay, readmissions and healthcare-associated cost^{7,8}. Therefore, strategies to reduce the incidence of SSI following colorectal surgery are important to improve overall patient outcomes, reduce healthcare-associated costs and provide value-based healthcare to surgical patients.

Since 2005, our institution has been an active participant of the American College of Surgeons (ACS) National Surgical Quality Improvement Program (NSQIP), and our SSI rates have been compared with other NSQIP centers; in 2006, we were found to be a high-outlier institution for SSI⁹. The ACS-NSQIP greatly facilitated our understanding of the reasons behind our high SSI rates, the patient profiles that are associated with SSIs, and how we can make improvements. This previously published work helped us to develop a Surgical Site Infection Prevention Bundle to reduce SSI rates after colorectal surgical procedures performed at the Cleveland Clinic. This bundle was introduced in February 2014. Between 2013 and 2015, 2250 abdominal colorectal surgical procedures were performed, including 986 (43.8%) during the prebundle period and 1264 (56.2%) after the bundle project. Patient characteristics and comorbidities were similar in both periods. The overall surgical site infection rate decreased from 11.8% prebundle to 6.6% at the bundle period ($P < 0.001$). Although a decrease for all types of surgical site infections was observed after the implementation, a significant reduction was achieved in the organ-space subgroup (5.5%–1.7%; $P < 0.001$). Since then, the elements of this bundle became the standard of care in all elective colorectal surgeries done at the Cleveland Clinic. The most important elements of the bundle include mechanical bowel preparation, antimicrobial antiseptic skin cleanser, prophylactic antibiotic (ceftriaxone + Flagyl) 1 hour prior to incision, wound irrigation with normal saline, and the usage of wound protector. The outcomes of this SSI prevention bundle was recently published¹⁰. Although this study was not designed to pinpoint the relative weight of each of these elements in reducing SSIs, participating colorectal surgeons at our institute accredit a big role for wound protectors and irrigation along with prophylactic antibiotics.

Key to the pathogenesis of SSI is the degree of intraoperative bacterial contamination of the surgical wound. Preventing contamination of the wound or reducing the bacterial load through the use of barrier wound protectors or intraoperative wound irrigation has shown significant promise individually and is an ongoing strategic focus to reduce wound infections after surgery¹¹⁻¹³. A similar role can be attributed to prophylactic antibiotics administered within one hour prior fist incision.

The importance of wound protectors and intraoperative wound irrigation can be elucidated by examining published meta-analyses. The first represented 6 randomized clinical trials (RCTs) and 1008 patients evaluated for the effect of wound protectors in reducing the risk of surgical site infection (SSI) after gastrointestinal surgery. A significant decrease in SSI rates (RR = 0.55, 95% confidence Interval (CI) 0.31-0.98, $P = 0.04$) was noted¹³. A more recent meta-analysis included eighteen randomized controlled trials with 3808 patients. The use of wound protectors was associated with the reduced incidence of overall SSI (OR 0.59; 95% CI 0.43-0.81; $z = 3.30$;

$p < 0.001$) and superficial SSI (OR 0.42; 95% CI 0.18-0.95; $z = 2.09$; $p < 0.04$). In addition, wound protectors successfully reduced the risk of SSI in clean-contaminated wounds (OR 0.67; 95% CI 0.46-0.98; $z = 2.06$; $p < 0.04$) as well as in contaminated wounds (OR 0.24; 95% CI 0.12-0.49; $z = 3.96$; $p < 0.0001$)¹¹. Based on that, the WHO global guidelines for the prevention of surgical site infection recommends the usage of wound protector devices in clean-contaminated, contaminated and dirty abdominal surgical procedures for the purpose of reducing the rate of SSI¹⁴.

The usage of intraoperative wound irrigation has also been shown to significantly reduce the risk of SSI via multiple RTC. A significant reduction in SSI rates after intraoperative wound irrigation with any solution was noted compared to no irrigation (OR = 0.54, 95 % CI 0.42; 0.69, $p < 0.0001$)¹³.

A surgical device that combines continuous wound irrigation and barrier protection will have an important SSI prevention advantage. CleanCision is a recently developed apparatus that serves this dual purpose and was found to reduce bacterial wound contamination in preclinical and clinical trials. A prospective multicenter pilot study was conducted by colorectal surgeons at 7 large tertiary-care referral centers in the USA¹⁵. The study was designed to evaluate the bacteriology of the wound incision edge when an investigational device (CleanCision wound protector) that combines continuous wound irrigation and barrier protection was used during colorectal surgery. A total of 97 patients (11 roll-in and 86 treatments) were enrolled in the study. All patients completed the 30-day follow-up. The 86 treatment patients were used for the primary analysis. Use of the study device was associated with a 71% reduction in enteric bacterial contamination (9.5% vs 33.3%, $P < 0.001$), and 66% reduction in overall bacterial contamination (11.9 vs. 34.5%, $P < 0.001$) at the protected incision edge versus the exposed incision edge. In addition, analysis of the skin organisms on the incision edge prior to device placement compared to the protected incision edge at the time of device removal demonstrated an 86% reduction after use of the study device (16.7 vs. 2.4%, $P < 0.001$). There were no deaths and no device-related adverse events reported in the study. There were 4 wound-related adverse events, other than SSI, reported: 1 skin necrosis, 1 non-infectious erythema, 1 hematoma and 1 wound opening up postoperatively. All 4 events were not device related as determined by the site investigator. Although SSI was not the endpoint that this study was designed to examine, the observed overall SSI rate was 1.2%, such rate is lower than reported at our institute for colorectal surgery (6.6%)¹⁵.

As part of our continuous effort to reduce SSI, additional measures such as CleanCision wound protector could bring our SSI rates even further. This will translate in better patient care and reduced health care cost.

Supported by the previously published multicenter clinical trial^{11, 13, 15}, this study aims to investigate the effect of using CleanCision wound protector on the rates of postoperative Surgical Site Infections in comparison to the current wound protector (Alexis O) being used at our institute.

2. STUDY OBJECTIVE

To evaluate the 30 day post-operative SSI rate in patients undergoing elective colorectal surgical procedures after intraoperative usage of Alexis O wound protector vs. CleanCision continuous irrigation wound protector.

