3.3 Statistical Considerations

Planned Data Analysis

Descriptive statistics will be computed for all variables including mean \pm standard deviation or median [25th, 75th percentiles] for continuous factors and frequency (percent) for categorical variables. Univariate analyses will be conducted to compare the distribution of pre-op characteristics across study groups using ANOVA for continuous variables and Chi-square or Fisher's exact test for categorical variables.

For purposes of statistical analysis, a subset analysis may be done based on laparoscopic vs. open procedures, patients with high risk for SSI, type of surgery, or other clinically significant co-factors. All data will be analyzed with the use of SAS (version 9.4, The SAS Institute, Cary, NC), SPSS statistical software (SPSS Inc., Chicago, IL), or R version 3.1.2 (www.R-project.org). A p-value <0.05 will be considered statistically significant.

Sample Size Calculations

The sample size calculation using estimates of SSIs from the Papaconstantinou et al. Multicenter trial. This study showed an incisional SSI rate of 1.2% in those that completed the protocol. In comparison, the incisional SSI rate using the current standard of care

practice at our institute is 4.8 %. On the other hand, the overall SSI rates in Papaconstantinou et al. multicenter trial is 3.7% and in the current standard of practice at the Cleveland Clinic, the overall SSI rate is 6.6%. We used these two estimates of SSI rates to calculate the sample size. Using the incisional SSI, we assumed a 3.6% drop rate if the study hypothesis is true. We are assuming equal-sized treatment groups and alpha = 0.05. Based on this assumption, a total of 277 subjects in each study group will be needed to achieve 70% power, 351 subjects in each study group will be needed to achieve 80% power, and 470 subjects will be needed to achieve 90% power. On the other hand, using the overall SSI rates and assuming a drop of 2.9%, a total of 716 subjects in each study group will be needed to achieve 70% power, 805 subjects in each study group will be needed to achieve 80% power, and 1219 subjects will be needed to achieve 90% power.

Based on the above, 351 patients will be enrolled in the study in each arm with a total of 702 patients.

Reporting of Results

Aggregate and anonymous, in text and table format, for publication in a medical journal.

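### No primary endpoint is named: the objective is any 30-day SSI, but 351 per arm is sized for incisional SSI and gives about 41% power for overall SSI at the plan's own rates

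*Combined protocol and SAP*

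**What the plan says.** - **Objective.** Section 2 is one sentence, "To evaluate the 30 day post-operative SSI rate in patients undergoing elective colorectal surgical procedures", comparing the two wound protectors. The closing aim of Section 1 also speaks of postoperative SSI without restriction.
- **Outcome recorded.** Section 4.4 records SSI by the protocol's definitions. Section 4.5 defines superficial, deep and organ/space SSI and does not say whether they are pooled.
- **Sample size.** Section 3.3 runs two calculations. For the first: "Using the incisional SSI, we assumed a 3.6% drop rate if the study hypothesis is true", giving 277, 351 and 470 per arm for 70%, 80% and 90% power. The second is made "using the overall SSI rates and assuming a drop of 2.9" percent, giving 716, 805 and 1219; in particular, "805 subjects in each study group will be needed to achieve 80% power". The conclusion is "Based on the above, 351 patients will be enrolled in the study in each arm with a total of 702 patients".
- **Planning rates.** Section 3.3 says of the multicentre pilot: "This study showed an incisional SSI rate of 1.2% in those that completed the protocol", and gives 3.7% as the pilot's overall rate. Section 1 says of the same pilot: "the observed overall SSI rate was 1.2%, such rate is lower than reported at our institute for colorectal surgery", setting 1.2% against the site's 6.6%.
- **Analysis.** The only between-group comparison that Section 3.3 specifies is of preoperative characteristics. No test of SSI between the arms is given.

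**The concern.** An unrestricted SSI objective, read with definitions that include organ/space infection, most naturally means all SSI. The number enrolled answers a different question, incisional SSI, and nothing in the text makes that the primary endpoint.

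Two things are at stake. If the trial is analysed as Section 2 reads and Section 3.3's overall rates are true, it will more often miss the assumed effect than find it, and a null result would say little. And with two SSI endpoints available and neither declared, whichever gives the better p-value can be presented as the answer.

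The mislabelled pilot rate makes this worse, because the reader cannot tell which rate the pilot supports for which endpoint.

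**Working it through.** **Inputs (Section 3.3).** Incisional: p1 = 0.048 (site), p2 = 0.012 (pilot). Overall: p1 = 0.066, p2 = 0.037. Alpha 0.05, equal arms. Neither the formula nor the sidedness is stated; the pooled-variance two-proportion formula, two-sided, fits five of the six stated sizes.

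**Formulas.** With d = p1 − p2, p̄ = (p1 + p2)/2, A = 1.960 × √[2p̄(1 − p̄)] and B = √[p1(1 − p1) + p2(1 − p2)]:

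- n per arm = (A + z_power × B)² / d²
- power = Φ[(d√n − A) / B]

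**Reproducing the plan's sizes.**

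- Incisional, 80%: A = 1.960 × √0.0582 = 0.4728 and B = √0.05755 = 0.2399. n = (0.4728 + 0.8416 × 0.2399)² / 0.036² = 351.3.
- Overall, 80%: A = 1.960 × √0.09770 = 0.6126 and B = √0.09728 = 0.3119. n = (0.6126 + 0.8416 × 0.3119)² / 0.029² = 910.6.

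| Endpoint | Power | Stated n per arm | Computed |
|---|---|---|---|
| Incisional, 4.8% vs 1.2% | 70% | 277 | 276.5 |
| | 80% | 351 | 351.3 |
| | 90% | 470 | 469.8 |
| Overall, 6.6% vs 3.7% | 70% | 716 | 716.3 |
| | 80% | **805** | **910.6** |
| | 90% | 1219 | 1218.5 |

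Only 805 fails. Power at 805 is 75.0%, and the formula's size for 75% power is 805.3, so it may be a 75% figure under an 80% label; that origin is inference. The unpooled formula gives 348.6 and 907.9 at 80%, which leads to the same conclusion.

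**Power at the adopted 351 per arm.** For overall SSI: (0.029 × √351 − 0.6126) / 0.3119 = (0.5433 − 0.6126) / 0.3119 = −0.222, and Φ(−0.222) = 0.412.

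| Rates | Source | Power (formula) | Exact enumeration, uncorrected chi-square |
|---|---|---|---|
| 4.8% vs 1.2% | Section 3.3, incisional | 80.0% | 83.0% |
| 6.6% vs 3.7% | Section 3.3, overall | 41.2% | 41.6% |
| 6.6% vs 3.0% | Assumed: full incisional drop, remainder unchanged | 60.7% | 62.0% |
| 6.6% vs 1.2% | Section 1's label for the pilot rate | 96.0% | 97.8% |

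The 3.0% is an assumption: the site's non-incisional part is 6.6 − 4.8 = 1.8 points, and 1.2 + 1.8 = 3.0. From a 6.6% control rate, 351 per arm has 80% power only for a fall to about 2.3%.

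The overall-SSI result is not sensitive to the test: 34.9% with Fisher's exact test, 34.7% with a continuity correction, and 53.7% even if one-sided.

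**The pilot rates.** Section 1 reports that "a significant reduction was achieved in the organ-space subgroup", from 5.5% to 1.7%, within the site's fall to 6.6%. So 6.6% includes organ/space SSI. If Section 3.3 is right that 1.2% is incisional, Section 1 compares unlike rates. The denominators also look different. Section 1 uses 86 patients: 1/86 = 1.2%, but 3/86 = 3.5% and 4/86 = 4.7%, so no whole number of cases gives 3.7%. A denominator of 81 or 82 would (3/81 and 3/82 both round to 3.7%).

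**Choice between endpoints.** Two million null trials were simulated with 351 per arm, 4.8% incisional plus a separate 1.8% other SSI, and an uncorrected chi-square test on each endpoint. Incisional or overall SSI is significant at 0.05 in 7.57% of trials, against 5.05% and 5.02% singly (correlation 0.844).

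**The case against.** The best case for the plan is that incisional SSI is plainly meant. Section 3.3 adopts the incisional number, the pilot evidence concerns the incision edge, and the only blinded assessment (Sections 4.2 and 4.3) is of wound photographs, which cannot show organ/space infection. On that reading power is 80% and the defect is one of wording. Nor does the plan claim 80% power for overall SSI at 351; it openly says that even 70% needs 716 per arm.

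Much of this is fair. The incisional reading is plausible, and the shortfall can be seen from the plan's own figures. But the intent has to be inferred against an objective, an aim and an outcome definition that all say SSI without restriction. A primary endpoint should not have to be inferred.

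Three qualifications stand:

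- The 7.6% applies only if either endpoint could be reported as the answer; the plan does not say that it would be.
- The 96% depends on a Section 1 label that Section 3.3 contradicts and that was not used for sizing. It shows what the contradiction is worth and is not a forecast.
- The 805 was not adopted and does not affect 351. It does understate the cost of the overall-SSI option by about 911 − 805 = 106 per arm.

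**Conclusion.** The concern holds. No primary endpoint is named, and the adopted size serves only one of two readings, and not the more natural reading of Section 2. At 351 per arm the plan has 80% power for incisional SSI. For overall SSI it has about 41% at Section 3.3's rates, so the assumed 2.9-point drop would be missed about 59% of the time. The 805 is wrong by the method that fits the plan's other five sizes. The pilot's 1.2% carries two incompatible labels, and which is right cannot be settled from the documents.

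These figures assume a two-sided 0.05 test, Section 3.3's rates, and outcome data from all 351 patients per arm; the plan states no allowance for loss.

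**What to change.** 1. **Name one primary endpoint in Section 2**, before any by-arm look at the data. The route that fits the planned size is 30-day incisional SSI (superficial plus deep, by Section 4.5), with overall and organ/space SSI secondary. That the number was sized for it is a practical reason, not a clinical one, so the sponsor should confirm that this is the question it wants answered.
2. **If all SSI is kept as primary**, either state power at 351 per arm as about 41% under Section 3.3's rates, or resize to about 911 per arm for 80%.
3. **In either case, in Section 3.3:** name the between-arm test of the primary endpoint and its sidedness, state the power for overall SSI, and correct 805 to about 911.
4. **Reconcile Sections 1 and 3.3** on the pilot's 1.2% and 3.7%, giving numerator and denominator for each, and compare like with like against the site's rates.

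**Cost.** The incisional route is wording in Sections 1, 2 and 3.3, with no extra patients; its price is openly reporting overall SSI as under-powered. All SSI at 80% power needs 2 × 911 = 1,822 patients, which is 1,120 more than the planned 702.

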3. SELECTION OF PATIENTS

3.1 Inclusion Criteria

- Patients 18 years old and above.
- Elective colorectal surgery with a planned resection including open or laparoscopic surgeries.
- Patients with a clean –contaminated, contaminated, or dirty wound classification
- Patients undergoing Standard of care SSI reduction bundle including Prophylactic AB and mechanical bowel preparation.
- Anticipated incision length of 3-17 cm

3.2 Exclusion Criteria

- Patients with a preexisting stoma.
- Patients with prior laparotomy within 15 days.
- Patients with an active infection or systemic antibiotic therapy within 1 week prior to surgery with the exception of preoperative antimicrobial prophylaxis.
- Emergent/ urgent surgery.

3.3 Statistical Considerations

Planned Data Analysis

Descriptive statistics will be computed for all variables including mean \pm standard deviation or median [25th, 75th percentiles] for continuous factors and frequency (percent) for categorical variables. Univariate analyses will be conducted to compare the distribution of pre-op characteristics across study groups using ANOVA for continuous variables and Chi-square or Fisher's exact test for categorical variables.

For purposes of statistical analysis, a subset analysis may be done based on laparoscopic vs. open procedures, patients with high risk for SSI, type of surgery, or other clinically significant co-factors. All data will be analyzed with the use of SAS (version 9.4, The SAS Institute, Cary, NC), SPSS statistical software (SPSS Inc., Chicago, IL), or R version 3.1.2 (www.R-project.org). A p-value <0.05 will be considered statistically significant.

Sample Size Calculations

The sample size calculation using estimates of SSIs from the Papaconstantinou et al. Multicenter trial. This study showed an incisional SSI rate of 1.2% in those that completed the protocol. In comparison, the incisional SSI rate using the current standard of care

practice at our institute is 4.8 %. On the other hand, the overall SSI rates in Papaconstantinou et al. multicenter trial is 3.7% and in the current standard of practice at the Cleveland Clinic, the overall SSI rate is 6.6%. We used these two estimates of SSI rates to calculate the sample size. Using the incisional SSI, we assumed a 3.6% drop rate if the study hypothesis is true. We are assuming equal-sized treatment groups and alpha = 0.05. Based on this assumption, a total of 277 subjects in each study group will be needed to achieve 70% power, 351 subjects in each study group will be needed to achieve 80% power, and 470 subjects will be needed to achieve 90% power. On the other hand, using the overall SSI rates and assuming a drop of 2.9%, a total of 716 subjects in each study group will be needed to achieve 70% power, 805 subjects in each study group will be needed to achieve 80% power, and 1219 subjects will be needed to achieve 90% power.

Based on the above, 351 patients will be enrolled in the study in each arm with a total of 702 patients.

Reporting of Results

Aggregate and anonymous, in text and table format, for publication in a medical journal.

4. STUDY DESIGN

This industry-initiated trial will be a prospective randomized controlled trial. The study will include patients undergoing elective colorectal surgical procedures. All patients will receive the standard of care SSI prevention bundle. Part of this bundle is the utilization of wound protectors. The current system used at Cleveland Clinic is Alexis wound protectors/retractors (Applied Medical, [name]). It provides 360° of circumferential, atraumatic dry retraction. Independent wound irrigation is also utilized. CleanCision is a novel FDA approved irrigating wound protector/ retractor that combines mechanical wound protection with an active continuous irrigation via microfluidic system that circulates the irrigation throughout the whole thickness of the protecting membrane. The safety and possible advantage of this new system has been shown through preclinical and clinical studies. Prescient Surgical, based in San Carlos, California, has an FDA marketing clearance for its CleanCision Wound Retraction and Protection System.

4.1 Consent

Patients will be identified prospectively by the treating surgeon according to the inclusion / exclusion criteria. Patients will be offered to participate in the study in the preoperative setting. The patient eligibility to participate in the study will be verified by the study team. The study details will be explained to the patient by a member of the study team. The consent conversation will take place in a private room and a sufficient time interval will be offered to allow the patient to comprehend the study details. Enrolled patients will be randomly assigned via REDCap in a 1:1 ratio to either the control arm (Alexis wound protector) or the intervention arm (CleanCision Wound retractor system). The randomization will be done by a delegated member of the study team. Consent will be documented in the medical record.

4.2 Study Process

Utilization of CleanCision wound protector/ Irrigation system is free of charge without extra financial charges to the enrolled patients.

The study team will confirm that patients are adhering to pre- intra- and post-operative standard of care SSI prevention bundle. The Bundle main elements are:

- Patient bathing with Hibiclens preoperatively.
- The patient use CHG (SAGE) wipes.
- Mechanical bowel preparation.
- Antibiotics Prophylaxis (ceftriaxone + Flagyl) given approximately 1 hour prior to incision. If the patient is allergic to above antibiotics, aztreonam or imipenem are used as prophylactic antibiotics.
- The usage of wound protector and the placement and removal of blue towels under the Alexis wound protectors for control cases.
- Use chlorhexidine gluconate and isopropyl alcohol for preoperative skin preparation
- Wound irrigated with 100cc of fresh saline.
- Separate instrument tray used for closing the incision.
- Gloves changed before closing the incision.
- Suction tip changed before closing the incision.
- Dressing left intact for 48 hours postop.

The usage of a wound protector along with wound irrigation intra-operatively is considered standard of care. This study entails utilizing two type of wound protectors, both are considered standard of care in terms of providing the baseline needed protection. Intra-operatively, either CleanCision Wound protector/ irrigation system or Alexis O wound protector will be chosen. Additional wound irrigation and washing with Normal Saline will be performed before skin closure as part of the standard of care. This will include both study groups (patients with Alexis O wound protectors and CleanCision wound protectors). In the CleanCision group, a broad spectrum antibiotic may be added to the irrigation fluid. Post-operatively, patients will be followed for wound infections according to the standard of care in the department of colorectal surgery. For patients undergoing colorectal procedures at the department of colorectal surgery, the timing of outpatient post-operative follow-up can be variable depending on the type of procedure performed, the treating surgeon, the patient place of residence, and the patient general medical condition. To avoid variability, patients will be asked to send a photographic documentation of the wound at day 7 ± 7 days and day 30 ± 7 days postoperatively to the study team. The photographs will be stored in the secure REDCap database. If a patient presents for follow-up at the outpatient clinic at the above time points and as part of standard of care, a photograph of the wound can be obtained during the outpatient visit by the study team member. The purpose of these photographs as well as the time points will be explained to the patient at the time study enrollment. Patients refusing or incapable of sending the photographs will not be enrolled in the study. For study enrolled patients' a reminder will be added to the hospital discharge note asking the patient to send the photographs to the above email address at the corresponding time points.

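### An optional antibiotic in the irrigation fluid of the CleanCision arm only, with no variable planned to record it, means a lower SSI rate could not be credited to the device alone

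*Combined protocol and SAP*

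**What the plan says.** Section 4.2 contains a one-arm permission: "In the CleanCision group, a broad spectrum antibiotic may be added to the irrigation fluid". It names no agent and gives no dose, rule for use or expected frequency.

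Section 4 describes the CleanCision device as providing "active continuous irrigation via microfluidic system that circulates the irrigation throughout the whole thickness of the protecting membrane", and the Alexis device as providing "circumferential, atraumatic dry retraction". The bundle in section 4.2 includes "Wound irrigated with 100cc of fresh saline", and the same section gives both groups a normal saline wash before skin closure. No antibiotic option is stated for irrigation in the control arm. The ceftriaxone and Flagyl prophylaxis in the bundle is given before incision in both arms and is a separate item.

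The Background ends by saying that "this study aims to investigate the effect of using CleanCision wound protector on the rates of postoperative Surgical Site Infections", with the current protector as comparator. Section 2 gives the contrast as "Alexis O wound protector vs. CleanCision continuous irrigation wound protector". Neither mentions an antibiotic.

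The intraoperative variables in section 4.4 are operating surgeon, incision length, surgical approach and device deficiencies. Section 3.3 plans no analysis or tabulation that refers to antibiotic irrigation.

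**The concern.** The outcome is infection, and the permitted additive is an anti-infective. If it is used, the CleanCision arm receives a component that the control arm is not offered and that the objective does not name. A report that follows the objective's wording would then present as an effect of the protector and its continuous irrigation something that may partly be an antibiotic effect.

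The plan also does not provide for a count of use. As written, the report could not be expected to say whether the tested strategy involved the antibiotic in almost no cases or in almost all of them. A surgeon or hospital deciding whether to adopt the device would need to know that.

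**Working it through.** **1. The texts side by side.**

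| Question | CleanCision arm | Alexis O arm |
|---|---|---|
| Irrigation through the protector (section 4) | Continuous | None; dry retraction |
| Wash before closure (section 4.2) | Saline | Saline |
| Antibiotic in irrigation fluid (section 4.2) | Optional | Not mentioned |
| Field for irrigant or additive (section 4.4) | None listed | None listed |
| Antibiotic irrigation in the aim or objective (sections 1 and 2) | Not named | Not named |

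**2. Whether an existing item already captures use.**
- *Bundle adherence.* This covers the elements listed in section 4.2. Its irrigation element is saline and its antibiotic element is prophylaxis before incision. An antibiotic in the device irrigant is neither. If the sentence refers to the pre-closure wash instead, an antibiotic wash might show as a departure from the saline element, but no agent would be asked for.
- *The catch-all for further SSI risk factors.* It does not name the irrigant, so capture would depend on whoever abstracts the data.
- *EPIC as the data source.* The documents do not say whether it holds the irrigant. Later retrieval is not planned; it is neither shown to work nor ruled out.

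**3. The plan's own design figure.** Section 3.3 sizes the trial on incisional SSI. For the device it uses the pilot: "This study showed an incisional SSI rate of 1.2% in those that completed the protocol". The control rate is 4.8%, so the assumed drop is 3.6 points. The standard formula with pooled variance under the null, two-sided alpha 0.05 and 80% power gives

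n = [1.960·√(2·0.030·0.970) + 0.842·√(0.048·0.952 + 0.012·0.988)]² / 0.036² ≈ 351.3 per arm.

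The plan states 351, so the figure reproduces. Nothing in this point disputes it. It is used only as a yardstick in step 4.

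**4. What could be at stake, under assumptions.** The documents give neither the share of CleanCision cases with antibiotic (f) nor its relative risk (RR) for SSI, so both are assumed here. Suppose also that the device by itself does nothing. The difference between arms produced by the antibiotic would then be 4.8 × f × (1 − RR) percentage points:

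| f | RR 0.75 | RR 0.50 | RR 0.25 |
|---|---|---|---|
| 10% | 0.12 | 0.24 | 0.36 |
| 50% | 0.60 | 1.20 | 1.80 |
| 100% | 1.20 | 2.40 | 3.60 |

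As a share of the 3.6-point design effect this runs from 0.12/3.6 = 3% to 3.6/3.6 = 100%. The table is not an estimate. It shows that the consequence runs from negligible to large, and that one of the two quantities deciding it, f, could be recorded at little cost but is not planned to be.

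**The case against.** The strongest reply is that the trial compares systems as delivered. Section 4.1 randomises to the CleanCision system, and section 4.2 openly says how that arm may be delivered, including the antibiotic. On that reading the randomised comparison is sound. This stands: nothing here invalidates the comparison or inflates type I error. A reader might infer that the antibiotic biases the trial outright. That would hold only for a device-only effect, which the protocol does not formally define. What remains is that the aim and objective do not describe the broader strategy.

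It can also be said that the arms already differ in several ways: the barrier itself, continuous irrigation, and blue towels under the Alexis protector in control cases. Separating components was never possible. That is fair, but the barrier and irrigation are what the device is said to be, and the towels are listed in the protocol as routine for control cases. The antibiotic is optional, and its use may vary from case to case without being counted.

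A further reply is that the catch-all for SSI risk factors could capture use. Its place under preoperative variables is no argument against this, since bundle adherence sits there too and includes intraoperative items. The remaining weakness is only that it does not name the irrigant.

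The sentence may also refer to the pre-closure wash rather than the device irrigant, because it directly follows the text about that wash. The one-arm difference is the same on either reading, and a field that covers both makes the ambiguity harmless.

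Lastly, recording use does not separate the two effects. That is correct, and it limits what the fix can claim.

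**Conclusion.** The point holds as a matter of interpretation and reporting. The plan permits an anti-infective in the irrigation of one arm only, does not plan to record it, and words its objective as if it were absent. To the extent it is used, a lower SSI rate could be credited to CleanCision as delivered, but not to the protector and its continuous irrigation alone.

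Three stronger readings are not supported:
- *That the device would deserve no credit.* Optional antibiotic use does not show that barrier and irrigation contribute nothing.
- *That the trial's result would be distorted by a known amount.* The size is unknown, and the range of 0.12 to 3.6 points above rests wholly on assumed use, an assumed antibiotic effect and an assumed null device effect.
- *That use could never be established.* The documents support only that recording is not planned.

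The conclusion rests on reading section 4.4 as the intended list of variables and on control irrigation being saline only, as section 4.2 describes it. If the antibiotic is never used, the problem disappears, but a planned record would be needed to show that reliably.

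**What to change.** 1. Add an intraoperative REDCap field, in both arms, for antibiotic in any wound irrigation, whether device irrigant or pre-closure wash (yes/no, agent). Report use by arm. Collecting it in both arms also confirms that control irrigation was saline.
2. If the option stays, word the objective and conclusion as CleanCision with optional antibiotic irrigation versus Alexis O with saline.

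The cost is one or two data fields, one table row and a wording change. Sample size, randomisation and treatment are untouched. The downside is a narrower claim, and the record would show use without isolating the antibiotic's effect.

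Barring the antibiotic, or allowing it equally in both arms, would remove the difference. Either one changes the intervention, so it is the sponsor's choice.
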